### 6.5 Subject Compliance

For this study, REPLAGAL is administered under controlled conditions at a clinical site; therefore, subject compliance with investigational product is anticipated to be high assuming 10% to 20% drop-out rate based on previous REPLAGAL trials.

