## 9. STATISTICAL CONSIDERATIONS

### 9.1 Statistical Analysis Process

The study will be analyzed by the sponsor or its designee.

The statistical analysis plan (SAP) will provide the statistical methods and definitions for the analysis of the efficacy and safety data, as well as describe the approaches to be taken for summarizing other study information such as subject disposition, demographics and baseline characteristics, investigational product exposure, and prior and concomitant medications. The SAP will also include a description of how missing, unused, and spurious data will be addressed.

To preserve the integrity of the statistical analysis and study conclusions, the SAP will be finalized prior to database lock.

All statistical analyses will be performed using SAS® (SAS Institute, Cary, NC 27513) version 9.4 or higher.

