## 9.5 Efficacy Analyses

Continuous variables will be summarized with descriptive statistics including the mean, standard deviation (SD), median, minimum and maximum. Categorical data will be summarized with the frequency and percentage of subjects falling within each category. Subsequently, longitudinal data will be analyzed using mixed-effects model for repeated measures, using both the mITT and PP sets (using the PP set will serve as a sensitivity analysis).

The observed values, the change from baseline, the change over time, and the percentage change from baseline for the efficacy measurements (eGFR, urine protein/creatinine ratio, plasma lyso-Gb3, LVMI, and LVEF) will be summarized by sex and visit.

Subject listings will be provided for clinical outcomes from the BPI-Short Form measurement.

Audiology results will be produced at baseline and (if applicable) for each post-baseline evaluation visit.

Audiology data will also be presented in the form of individual subject listings.

Efficacy analyses will be based on the mITT set, with the PP set as a sensitivity analysis.

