6.0 STATISTICAL ANALYSIS

6.1 General Considerations

All statistical analyses will be performed using SAS[®] (SAS Institute, Cary, NC 27513) version 9.4 or higher.

Baseline values are defined as the last observed value before the first dose of study medication.

Means and medians will be presented to 1 more decimal place than the recorded data. The standard deviations (SDs) will be presented to 2 more decimal places than the recorded data. CIs intervals will be presented using the same number of decimal places as the parameter estimate.

Continuous variables will be summarized with descriptive statistics including the mean, standard deviation (SD), median, minimum and maximum. Categorical data will be summarized with the frequency and percentage of subjects falling within each category. Subsequently, longitudinal data will be analyzed using mixed-effects model for repeated measures (MMRM), using both the mITT and PP sets (using the PP set will serve as a sensitivity analysis).

The observed values, the change from baseline, the change over time, and the percentage change from baseline for the efficacy measurements (eGFR, urine protein/creatinine ratio, and plasma lyso-Gb3) will be summarized by sex and visit.

Subject listings will be provided for clinical outcomes from the BPI-Short Form measurement.

Audiology results will be produced at baseline and (if applicable) for each post-baseline evaluation visit.

Audiology data will also be presented in the form of individual subject listings.

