6.5.2 Secondary Endpoints Analysis

Secondary efficacy analysis

Continuous variables will be summarized with descriptive statistics including the mean, standard deviation (SD), median, minimum and maximum. Categorical data will be summarized with the frequency and percentage of subjects falling within each category. Subsequently, longitudinal data will be analyzed using mixed-effects model for repeated measures (MMRM), with covariates baseline, age and time, and an unstructured (UN) covariance structure. In case the model does not converge, this specific analysis will not be performed. Both the mITT and PP sets (using the *PP* set will serve as a sensitivity analysis) will be used in these analyses.

The observed values, the change from baseline, the change over time, and the percentage change from baseline for the efficacy measurements (eGFR, LVMI and LVEF), and urine protein/creatinine ratio will be summarized by sex and visit.

Figures of individual for the observed values of eGFR, LVMI, lyso-Gb3 and urine protein/creatinine ratio and figures of individual for the change from baseline of lyso-Gb3 and

TAK675-3001	Page 18 of 27
Statistical Analysis Plan Amendment 1	1-Feb-2024

urine protein/creatinine ratio will be generated by visit. Figures of mean (\pm SD) eGFR split by eGFR group at baseline and mean (\pm SD) LVMI split by LVMI group at baseline will be generated by visit. The observed values, the change from baseline, the change over time, and the percentage change from baseline for eGFR split by eGFR group at baseline and LVMI split by LVMI group at baseline will be summarized by sex and visit. The mITT sets will be used in these analyses.

Subject listings will be provided for clinical outcomes from the BPI-Short Form measurement. Questions from BPI short form includes 2 subscales: Pain severity and pain interference. Pain severity from questions 3 to 6 with score range 0 (no pain) to 10 (pain as bad as you can image) and pain interference from questions 9A to 9G with score 0 (does not interfere) to 10 (completely interferes). For BPI short form, impute pain severity and pain interference question scores as 0 for subjects selected Q1 as "No pain" and no corresponding answer responded for pain severity and pain interference questions. For both subscales, the average score of all questions from that subscale will be imputed if missing.

Audiology results will be produced at baseline and (if applicable) for each post-baseline evaluation visit.

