6.5.2.4 Sensitivity Analysis

Longitudinal data (eGFR, urine protein/creatinine ratio, lyso-Gb3, LVMI and LVEF) will be analyzed using a mixed-effects model for repeated measures (MMRM), using the PP set.

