9.2.4 Handling of missing data

Imputation of missing data post-baseline will be employed using last observation carried forward (LOCF) for the endpoints of the change from baseline to subsequent time points in eGFR, LVMI, LVEF, lyso-Gb3 and urine protein / creatinine ratio. No data imputation will be done for the categorical analyses of the BPI (short form).

Imputation of missing dates 9.2.5

Any date that is collected only as MONTH / YEAR, e.g., date of birth, the 15th of the month will be imputed.

If AE start date is partial, the following imputation will be done:

- If day is missing, impute 1st of the month
- If day and month are missing, impute 01 July. However, this should be checked not to be later than the AE stop date. If AE stop date is available, the 1st of the month of the AE stop month should be imputed,

If AE stop date is partial, the following imputation will be done:

- If day is missing, impute end of the month $(30^{\text{th}} \text{ or } 31^{\text{st}})$
- If day and month are missing, impute 31 Dec.

If AE stop date is missing (i.e., AE still ongoing), and AE start date has missing day and month, and imputed AE start date per above rules (01July) is after date of death (DTHDT) or end of study date (EOSDT) then "01Jan" will be imputed as AE start date.

If imputed stop date is after date of death (DTHDT) or end of study date (EOSDT), AE end date will be imputed as date of death (DTHDT) or end of study (EOSDT).

The same rules above (for AE date imputation) will be followed for prior / concomitant medications and medical history.

TAK675-3001	Page 27 of 27
Statistical Analysis Plan Amendment 1	1-Feb-2024

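### SAP 6.5.2 drops the MMRM if its only covariance structure does not converge; a stated fallback would protect the PP sensitivity estimate for the five-visit measures

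*SAP*

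**What the plan says.** SAP 6.5.2 fits the MMRM "with covariates baseline, age and time, and an unstructured (UN) covariance structure". The next sentence gives the rule for failure: "In case the model does not converge, this specific analysis will not be performed". The paragraph covers both the mITT and the PP set.

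Three other places plan the same model without that condition:

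- SAP 6.1: "Subsequently, longitudinal data will be analyzed using mixed-effects model for repeated measures (MMRM), using both the mITT and PP sets".
- SAP 6.5.2.4, for eGFR, urine protein/creatinine ratio, lyso-Gb3, LVMI and LVEF: these data "will be analyzed using a mixed-effects model for repeated measures (MMRM), using the PP set".
- Protocol 9.5: "Subsequently, longitudinal data will be analyzed using mixed-effects model for repeated measures, using both the mITT and PP sets".

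Protocol 9.1 says that the SAP "will provide the statistical methods and definitions". Neither document names a second covariance structure, and neither says whether a singular covariance estimate counts as non-convergence.

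**The concern.** An unstructured covariance is the most demanding choice for a study of about 20 subjects, and the SAP pairs it with a rule that removes the analysis on failure. The PP set is drawn from the mITT set, so it can only be the same size or smaller. The PP fit could therefore fail while the mITT fit is reported. The model-based comparison that SAP 6.5.2.4 plans would then be missing for that measure. Picking a simpler structure after seeing the failure would be a data-driven choice; an order fixed in advance avoids it.

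**Working it through.** The plan gives no convergence figure to reproduce, so the check asks when the stated model can be estimated.

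**Inputs.** Planned subjects: 20 (SAP 4.0). Post-baseline visits: five (Weeks 8, 16, 28, 40, 52) for eGFR, urine protein/creatinine ratio and lyso-Gb3, and two (Weeks 16, 52) for echocardiography (Protocol Table 1). Dropout: Protocol 6.5, "assuming 10% to 20% drop-out rate based on previous REPLAGAL trials"; dropouts are not replaced (Protocol 7.3). Expected PP size: not given.

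**Covariance parameters.** Unstructured: T(T+1)/2. Heterogeneous compound symmetry: T+1. Compound symmetry: 2.

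- T = 5: 5×6/2 = 15, against 6 and 2.
- T = 2: 2×3/2 = 3, against 3 and 2.

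**Minimum number of complete subjects.** A singular residual covariance is attainable when some combination of the five visit values is fitted exactly in every complete subject by an intercept, baseline and age. The matrix [Y, 1, baseline, age] has 5 + 1 + 2 = 8 columns, so this always happens with 7 or fewer complete subjects. The count is the same for linear and categorical time. In 200 simulated data sets per size, the singular solution existed in 200/200 at n = 3 to 7 and 0/200 at n = 8, 9 and 10. For two visits the matrix has 5 columns, and the solution existed only at n = 4 and below.

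**Expected complete subjects.** With set size n, dropout d and an assumed chance m of missing any one visit, the expected number is n(1−d)(1−m)^5. At d = 0.20, with 0.95^5 = 0.774 and 0.90^5 = 0.590:

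| n | m = 0 | m = 5% | m = 10% |
|---|---|---|---|
| 20 | 16.0 | 12.4 | 9.4 |
| 16 | 12.8 | 9.9 | 7.6 |
| 12 | 9.6 | 7.4 | 5.7 |
| 10 | 8.0 | 6.2 | 4.7 |
| 8 | 6.4 | 5.0 | 3.8 |

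**REML simulation, dropout only.** Settings: five visits, 20% dropout, 60 runs each. Ranges cover two assumed correlation patterns, AR(1) 0.7 and compound symmetry 0.9. Failure means a singular estimate (smallest/largest eigenvalue below 1e-6) or no convergence.

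| n | Unstructured, observed data | Unstructured, LOCF data |
|---|---|---|
| 20, 16, 12 | 0 | 0 |
| 10 | 1–2 | 0 |
| 8 | 54–58 | 2–8 |
| 7 | 59–60 | 59–60 |

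Both columns are shown because SAP 9.2.4 applies LOCF to change from baseline in these measures, but the SAP does not say whether the MMRM uses the filled data. Heterogeneous compound symmetry and compound symmetry failed in 0 of 60 at n = 8 and n = 7 in every setting. Two-visit unstructured fits failed in 0 of 60 at n = 20, 8 and 7.

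**Adding intermittent gaps (observed data, AR(1) 0.7, 20% dropout).** Singular unstructured fits:

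- n = 20 and n = 16, 5% gaps: 0/20 each.
- n = 12: 4/20 and 1/10 in two batches at 5% gaps; 11/20 and 6/10 at 10%.
- n = 10, 10% gaps: 17/20.

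A second implementation (Fisher scoring, at most 50 iterations, 20% dropout, correlation 0.7 or 0.95 per 12 weeks) counted runs that did not converge: 1 of 60 at n = 20 and 4–5 of 60 at n = 16 with 5% gaps, and 28–31 of 60 at n = 12 with 10% gaps. Compound symmetry converged in every run.

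**Reading this back to the PP set.** Starting from 20, a PP set of 12 means 20−12 = 8 exclusions. A PP set of 8 to 10 means 10 to 12.

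**The case against.** The strongest reply is that the rule is itself pre-specified. It says what happens on failure, and declining to report a 15-parameter fit that fails is defensible where nothing is tested and the sample size rests on feasibility. That stands as a reason to rate the point low, but it does not bring back the planned estimate.

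The counted failures are also mostly singular estimates, while the SAP speaks only of non-convergence. This stands too. SAS was not run, and whether a singular solution is reported as non-convergence depends on the software: one implementation above mostly returned singular fits, and the other counted runs that did not converge. The rates are therefore not rates at which the SAP's rule would fire.

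The PP scenario has no documentary basis beyond the definition of the set. The documents expect 10% to 20% dropout and say nothing about how many subjects will have major deviations. If LOCF data feed the model, intermittent gaps matter little and the set would have to fall to about 7.

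Finally, the choice of fallback structures is partly taste. That is fair; what matters is that one order is fixed beforehand.

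**Conclusion.** The point holds as a minor one. The SAP gives a single covariance structure and no fallback. With five visits, the model cannot give a non-singular estimate from fewer than 8 complete subjects. On observed data a failed or singular fit becomes plausible in a PP set of about 8 to 10 with dropout only, or about 12 with intermittent gaps. The 8-subject floor is algebra. The set sizes depend on assumed correlations, dropout timing and gap rates.

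Four stronger readings are tempting and not supported:

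- **The mITT estimates are in danger.** At n = 16 to 20, failures were absent or few. The one borderline cell in the table is n = 16 with both a further 20% dropout and 10% gaps.
- **The SAP breaches the protocol.** Protocol 9.1 leaves methods to the SAP, so the extra condition is a detail of method.
- **The whole mITT/PP comparison would be lost.** The SAP 6.5.2 paragraph uses both sets for its analyses, which include descriptive statistics. Only the model-based PP estimate would go.
- **The model must fail in children.** SAP 6.5.4 splits efficacy data by age group but does not say the MMRM is refitted within groups, and age is already a covariate.

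LVMI and LVEF, with 3 parameters, are not a practical concern. No hypothesis is tested (SAP 3.1), and the primary result on serious TEAEs is untouched.

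**What to change.** Replace the sentence in SAP 6.5.2 with:

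> If the UN model does not converge, or gives a singular covariance estimate or a Hessian that is not positive definite, it will be refitted with heterogeneous compound symmetry and, if that also fails, with compound symmetry. The same order applies to the mITT and PP fits, and the structure used will be named in the table. If the two sets end with different structures, the mITT model will also be shown with the structure used for the PP set.

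The last sentence keeps a change of population from being mixed with a change of covariance model. For LVMI and LVEF the heterogeneous step has the same 3 parameters as UN, so compound symmetry is the effective fallback.

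The cost is three sentences and standard SAS options. A simpler covariance adds an assumption, but it is used only where the alternative is no usable model. One extra mITT fit is needed if the structures differ.

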#### **CONFIDENTIAL**

Takeda

REPLAGAL

ADA=anti-drug antibody; AE=adverse event; β-hCG=beta-human chorionic gonadotropin; BPI=Brief Pain Inventory; ECG=electrocardiogram; eGFR=estimated glomerular filtration rate; EOT=end of treatment; EOW=every other week; HCV=hepatitis C virus; IRR=infusion-related reaction; lyso-Gb3=globotriaosylsphingosine; PK=pharmacokinetic; SAE=serious adverse event

- a Screening procedures can be performed over multiple days within a period of up to 42 days following the subject's (or the subject's parent(s)/legally authorized representative) signature of the informed consent form.
- bAll baseline procedures and evaluations must be completed prior to the first REPLAGAL infusion and will be performed at the clinical site. Serum chemistry, hematology, urinalysis, and ECG performed at screening within 7 days prior to baseline visit may be used as the baseline.
- c During the treatment period, all study assessments and procedures should be completed on the day(s) of the scheduled visit.
- dThe REPLAGAL infusions are to be administered at the clinical site.
- eProcedures and evaluations to be performed at site visits will occur at the clinical site.
- f The safety follow-up period (end of study) is 14 days (+7 days) following EOT infusion (or the last infusion for discontinued subjects). During this period, there will be a telephone call/scheduled visit to query for AEs, SAEs, and concomitant medications. Subjects who experienced SAEs, or mild, moderate, or severe AEs may be requested to visit the clinical site for further examination. All AEs and SAEs that are not resolved at the time of this contact will be followed to closure.
- gFor subjects who discontinue the study early, all EOT assessments and procedures should be completed except for dose calculation and REPLAGAL infusion.
- hInformed consent must be obtained prior to performing any study-related procedures.
- i Fabry disease diagnosis will be confirmed at screening by medical record.

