6.3 Demographic and Other Baseline Characteristics

6.3.1 Demographics

Demographic and Baseline characteristics will be summarized using either descriptive statistics or frequency distributions, as appropriate.

The following demographic and baseline characteristics will be summarized:

- age (years) at Informed Consent
- age (years) at baseline
- age (years) at treatment start
- Fabry disease diagnosis (years) at Informed Consent
- weight (kg) and height (cm)
- BMI (kg/m²)
- Sex
- race
- eGFR
- eGFR group at baseline (30-<60 mL/min/1.73m², 60-<90 mL/min/1.73m², 90-<135 mL/min/1.73m², ≥135 mL/min/1.73m²)
- LVMI
- LVMI group at baseline ($<50 \text{ g/m}^{2.7}$, $\ge 50 \text{ g/m}^{2.7}$)
- LVEF
- urine protein / creatinine ratio
- baseline pain or without pain (Yes/No)
- baseline pain severity score

TAK675-3001	Page 16 of 27
Statistical Analysis Plan Amendment 1	1-Feb-2024

• baseline pain interference score

A listing will be created to show all the demographics and baseline characteristics for each subject in the ITT and mITT. The demographic and baseline characteristic summary tables will be presented for subjects 2 to <12 years at the time of signing ICF, 12 to <18 years at the time of signing ICF, <18 years at the time of signing ICF, \geq 18 years at the time of signing ICF, and the overall population.

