6.6.3 Other Safety Analysis (if applicable)

Tabular summaries of other safety endpoints (eg, vital signs, blood tests, concomitant medications [coded using the World Health Organization Drug Dictionary], anti-agalsidase alfa antibody status, and infusion information) will be produced at baseline and, if applicable, for each postbaseline visit.

Changes in the results of physical examination from the baseline will be presented by visit and body system in the form of a shift table.

TAK675-3001	Page 21 of 27
Statistical Analysis Plan Amendment 1	1-Feb-2024

The observed values and the change from baseline for ECG parameters (PR, QRS, QT, QTc, and heart rate) will be summarized by visit. The number of subjects with normal and abnormal ECG results during the study period will be summarized by visit in the form of a shift table.

Laboratory data will be listed by subject. Subjects with newly occurring abnormalities outside the normal range will be flagged, listed separately, and summarized. The mean change from baseline in laboratory values or a shift table also will be provided at each visit. Change from baseline will be calculated by subtracting the baseline value from the post-baseline value.

Vital sign data will be listed by subject. Mean changes from baseline for vital sign data will be summarized. Subjects with notable abnormal values will be identified and listed separately along with their values – notable abnormal values will only be identified in adult (\geq 18 years) according to the following thresholds:

Sitting and supine		alia
Systolic BP (mmHg)	High and increase	\geq 140 and increase of \geq 20 from baseline value
	Low and decrease	<90 and decrease of >20 from baseline value
Diastolic BP (mmHg)	High and increase	\geq 90 and increase of >15 from baseline value
	Low and decrease	50 and decrease of >15 from baseline value
Pulse rate (bpm)	High and increase	\geq 100 and increase of >15 from baseline value
	Low and decrease	<45 and decrease of >15 from baseline value

The number and percentage of subjects reporting at least one use of concomitant medication during the study will be reported.

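### The split eGFR and LVMI tables measure change from the same single baseline reading that defines the groups, so regression to the mean biases these supportive outputs in both directions

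*SAP*

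**What the plan says.** SAP 6.3.1 defines the groups by fixed cuts on the baseline value. For eGFR they are "eGFR group at baseline (30-<60 mL/min/1.73m²", then 60-<90, 90-<135 and >=135; for "LVMI group at baseline" they are <50 and >=50 g/m^2.7.

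SAP 6.1 takes a single reading as baseline: "Baseline values are defined as the last observed value before the first dose of study medication". SAP 6.6.3 gives the arithmetic of change, written there for laboratory data: "Change from baseline will be calculated by subtracting the baseline value from the post-baseline value".

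SAP 6.5.2 then summarises observed values, change and "percentage change from baseline for eGFR split by eGFR group at baseline and LVMI split by LVMI group at baseline" by sex and visit in the mITT set. It adds mean (±SD) figures for eGFR by baseline eGFR group, and "LVMI split by LVMI group at baseline will be generated by visit". The change log in SAP 9.1 describes the added figures and table as supporting the efficacy analysis.

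The trial is single-arm (SAP 2.0) and tests no hypothesis (SAP 3.1). Protocol Table 1 schedules eGFR at both screening and baseline, calculated by the central laboratory. Echocardiography is scheduled at baseline, Week 16 and Week 52 and is read locally. Footnote b to Table 1 allows one sample to serve twice: "Serum chemistry, hematology, urinalysis, and ECG performed at screening within 7 days prior to baseline visit may be used as the baseline". Neither document mentions regression to the mean or puts a caution on the split outputs.

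**The concern.** A subject falls in an extreme group partly because of the true level and partly because of measurement error or day-to-day variation in that one reading. The second part does not persist, so later readings drift back towards the population mean with no change in the patient. Because the same reading is also subtracted, the drift enters the change score in full. It also shows in the mean figures, where the group's baseline point is displaced and later points are not. A control arm would show the same drift and allow it to be removed; here there is none.

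What is at stake is how two sets of descriptive tables and figures are read. The groups of most clinical interest, impaired eGFR and raised LVMI, are pushed in the favourable direction, while the high-eGFR and low-LVMI groups are pushed in the unfavourable direction. Either could be taken for a treatment pattern that depends on baseline severity.

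**Working it through.** The plan states no SD, effect size or power, so there is no planned figure to reproduce. The values marked as assumed below are not from the documents.

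**Model.** True value t is constant (zero true change). Screening s, baseline b and follow-up f each equal t plus independent normal error. With between-subject SD σ_b, within-subject SD σ_w and ICC = σ_b²/(σ_b² + σ_w²), and before any eligibility cut,

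E[f - b | group] = -(1 - ICC) × (E[b | group] - μ).

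**LVMI.** Assumed: μ = 45, σ_b = 12, σ_w = 3 / 5 / 7 g/m^2.7. The cut of 50 is from SAP 6.3.1. For σ_w = 5:

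- S = √(144 + 25) = 13; ICC = 144/169 = 0.852; a = (50 - 45)/13 = 0.385; φ(a) = 0.3705; P(b >= 50) = 0.350.
- >=50 group: -0.148 × 13 × 0.3705/0.350 = -2.0.
- <50 group: +0.148 × 13 × 0.3705/0.650 = +1.1.

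| σ_w | >=50 group | <50 group |
|---|---|---|
| 3 | -0.8 | +0.4 |
| 5 | -2.0 | +1.1 |
| 7 | -3.7 | +2.1 |

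Simulation (2,000,000 draws) agrees. The within-group change between two post-baseline echoes is 0.00 in every scenario, because neither reading was used to classify.

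**eGFR, adults.** Assumed: μ = 90, σ_b = 22, σ_w = 4 / 6 / 8. From the protocol: the 45 to 120 window (5.1), applied again at baseline (8.1.2). Simulated mean change, 2,000,000 draws per scenario:

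| Group | Grouped by baseline | Grouped by screening |
|---|---|---|
| <60 (45-<60 in adults) | +1.5 / +3.2 / +5.4 | -0.3 / -0.8 / -1.4 |
| 60-<90 | +0.4 / +0.9 / +1.6 | 0.0 / 0.0 / -0.1 |
| >=90 (up to 120) | -0.6 / -1.2 / -2.1 | +0.2 / +0.4 / +0.8 |
| All adults, unsplit | +0.1 / +0.1 / +0.2 | same |

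The direction in the middle group depends on where the assumed mean lies. The residue under screening grouping arises because the eligibility window is applied again to the baseline value.

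**Sensitivity.** With σ_b = 20, μ = 80 or 90 and σ_w = 4 to 10, the <60 group shows +1.4 to +8.5 and the >=90 group -0.6 to -4.9. For LVMI with μ = 45 or 50 and σ_b = 12 or 15, the >=50 group shows -0.5 to -3.7 and the <50 group +0.3 to +2.7.

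**Cell size.** Twenty subjects with at least 25% under 18 leave at most 15 adults. Under the main assumptions 7.2% to 7.6% of adults fall below 60, so 15 × 0.072 to 0.076 = about 1.1 adults. The cell has no adult with probability (1 - 0.072)^15 to (1 - 0.076)^15, about 33% to 31%. The SD of one subject's change in that cell is 5.5 to 10.6.

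**With true decline.** If every adult truly loses 2 mL/min/1.73 m² (μ = 90, σ_b = 20), a non-empty <60 group shows a gain in 47% of trials at σ_w = 4, rising to 73% at σ_w = 10.

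**The case against.** The strongest reply is that little rests on these outputs. The primary endpoint is serious TEAEs, no hypothesis is tested, and the listed Week 52 eGFR endpoint is unsplit. Unsplit summaries, individual plots and an MMRM with baseline as a covariate are all planned. Grouping by baseline severity is ordinary descriptive practice. All of this stands, and it limits the point to the split tables and mean figures.

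It is also fair that noise will swamp the bias in a low-eGFR cell of about one adult, and that the sizes are assumed. The simulation covers adults only: children have no eGFR entry window, so nothing is estimated for them. Since adults are capped at 120, the >=135 group can only be paediatric.

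A reader might infer that the tables will show renal gain and LV mass regression even if the drug does nothing. The documents do not support that. The protocol describes Fabry disease as slowly progressive, so without an effect eGFR may be falling, and regression to the mean may hide only part of the fall. Nor does the artefact favour the drug throughout. Under these assumptions the >=90 group (about 45% of adults) and the LVMI <50 group (about 65% of subjects) are biased against it.

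The reply does not remove the mechanism. The MMRM has no baseline-group term and does not feed the split outputs, and nothing tells their reader what to expect.

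**Conclusion.** The point holds for the split change tables and mean figures in SAP 6.5.2, as a bias in both directions. Under the main assumptions and zero true change it is about +1.5 to +5.4 mL/min/1.73 m² for adults below 60, -0.6 to -2.1 for adults at or above 90, -0.8 to -3.7 g/m^2.7 for LVMI >=50 and +0.4 to +2.1 for LVMI <50. These sizes rest on assumed means and SDs and on independent normal errors; only the direction follows from the plan itself. Unsplit change moves by 0.2 or less for eGFR, and the primary endpoint is untouched. This is a cheap improvement to supportive outputs. It does not undermine the trial's efficacy endpoints.

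A reader might also infer that the protocol's permission to reuse screening samples as baseline must be withdrawn. It need not be: subjects whose screening sample served as baseline can be flagged.

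**What to change.** Amend SAP 6.3.1 and 6.5.2 only.

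- **eGFR:** for the split tables and figures, define the group by the screening central-laboratory eGFR where it is a separate sample from the baseline value. Keep baseline as the reference for change. Flag subjects whose screening sample served as baseline.
- **LVMI:** only one pre-dose echo is scheduled, so keep the baseline groups. Beside change from baseline, show the Week 16 to Week 52 change within group, using subjects with both echoes observed. The LOCF rule in SAP 9.2.4 would otherwise enter zeros.
- **Footnote:** on every split output, give cell sizes and state that change from baseline by baseline group includes regression to the mean in both directions.

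The cost is SAP wording, re-running two sets of tables and figures, and one footnote; all the data are already scheduled. There are three downsides. Subjects near a cut-point change group: in the simulation, 26% to 50% of adults with baseline below 60 have a screening value in another group. A small opposite residue remains in the low-eGFR group, about -0.3 to -1.4. The Week 16 to Week 52 LVMI change omits any early effect, which is why it sits beside change from baseline and does not replace it.
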